## 6 Participants

### 6.1 Inclusion criteria

- Newly diagnosed women with GDM referred to Department of Obstetrics Herlev Hospital
- Women diagnosed with GDM based on a 2-hour OGTT plasma glucose value  $\geq 9.0$  mmol/l
- Women diagnosed with GDM based on at least 2 plasma glucose measurements above targets (either pre-prandial  $\geq 6.0$  mmol/l, or 2-hours postprandial  $\geq 8.0$  mmol/l)
- GA at GDM diagnosis  $\leq 34$
- Women with an estimated probability of  $\geq 20\%$  for initiating insulin treatment during pregnancy. The estimated probability is based on a logistic regression model developed at SDCC and includes the following variables: prepregnancy BMI, GA at GDM diagnosis, and HbA1c at GDM diagnosis. In cases where HbA1c has not been measured during the initial

visit with the dietitian (screening visit), prepregnancy BMI and GA at the time of diagnosis will be used to estimate the probability of initiating insulin therapy.

- Provided voluntary written informed parental consent in Danish or English or after translation by an interpreter for non-Danish and non-English speaking parents

## 6.2 Exclusion criteria

- Bariatric surgery
- Other intercurrent illness (e.g., cancer, ulcerative colitis) as judged by the medical experts
- Uncontrolled medical issues, as judged by the investigators
- Concomitant participation in other clinical trials that could interfere with the INTENSE-GDM trial as evaluated by the investigators
- Unable to understand the informed consent and procedures regardless of the language spoken

## 6.3 Criteria for withdrawal

One or more of these criteria will result in withdrawal of the participant from the study:

- A participant withdraws the informed consent
- A participant's general condition contraindicates continuing the study as judged by the investigators or medical experts
- Other reasons determined by the investigator

## 7 Examinations

All patients found eligible for inclusion in the study will be invited to a first study visit (V1) for collection of baseline measurements according to study specific SOPs. Subsequently, all participants will be randomised to one of the two study groups. All examinations will be performed in the outpatient diabetes clinic at SDCC. Study visits and examinations are described in detail in table 2 below, in the current section and section 5.4.

**Table 2:** Schematic overview of study visits

Visit	V0	V1	V6
Patient-related information			
Informed consent	X		
Assessment of in- and exclusion criteria	X		
Medical history	X		
Dietary history		X	X
Medication use		X	X
Randomisation	X		
Clinical efficacy outcomes			
Insulin use			X
Insulin dose (IE per kg body weight)			X
Time to insulin (days) from study allocation until prescription			X
Diet history interview		X	X
HbA1c		X	X
Body weight and height (height only at V1)		X	X
7-point SMBG		X	X
Questionnaires			
Socio-economic and ethnic characteristics		X	
Well-being (WHO-5)		X	X
Diabetes Diet-Related Quality of Life (DDRQOL)		X	X
Health Care Climate Questionnaire (HCCQ)		X	X
Perceived Competence in Diabetes Scale (PCDS)		X	X
Diabetes Treatment Satisfaction Questionnaire (DTSQ)		X	X
Pregnancy Physical Activity Questionnaire (PPAQ)		X	X

Abbreviations: SMBG, Self-Monitored Blood Glucose; V0, Screening, V1, data collected at baseline; V6, data collected pre-delivery.

### 7.1 Clinical examination

Body weight and height will be measured to the nearest 0.1 kg and 0.1 cm, respectively with calculation of BMI (kg/m^2) at the baseline visit (V1). Body weight will be measured with the participant wearing light indoor clothes and no shoes after emptying the bladder. Height is measured using a wall-mounted stadiometer with the participants not wearing shoes and with the heels, buttocks and upper part of the back remaining in contact with the wall/back of the stadiometer. Body weight at V6 will be recorded based on data from the patients' medical records. GA at the time of the registered body weight measurement in EMR will be recorded.

## 7.2 Blood samples

HbA1c will be measured in a non-fasting condition. The routine HbA1c measurement performed shortly after referral to Department of Obstetrics at Herlev Hospital will be recorded at V1, and HbA1c measured closest to delivery (GA recorded) will be recorded at V6. Laboratory analyses of blood samples will be performed in the laboratory at Herlev-Gentofte Hospital by skilled laboratory technicians.

## 7.3 Electronic medical record data

The written consent provides the trial investigators, the sponsor, the sponsor's representatives, and regulatory authorities direct access to obtain information from the patient's medical records, including electronic records, with the purpose of reviewing information regarding the participant's health condition. This access is necessary for conducting the research project and for regulatory oversight, including self-regulation, quality control, and monitoring, which they are obligated to perform. According to planned and described procedures, the research dietitians will access the participant's medical record to collect information relevant to the study as described under screening (assessment of in- and exclusion criteria), collection of medical history, concomitant medications, and clinical outcomes from referral until discharge after delivery. The purpose of obtaining information from the medical records is to assess whether the women is eligible for inclusion, to describe the study population, and report study outcomes related to pregnancy and child delivery.

The following data from the mother's and infant medical records and The National Patient Register will be collected (see Table 1 for details about data sources):

### Background data

Age

GA at GDM diagnosis and referral to the Department of Obstetrics

Method for diagnosing GDM (OGTT or 3-days SMBG monitoring)

OGTT value, mmol/l at diagnosis

Number of pregnancies, n

Multiple pregnancy

Previous GDM

Prepregnancy BMI, kg/m^2

Hypertensive disorders of pregnancy

Pregestational hypertension

Pregestational dyslipidaemia

Diet-affecting diseases e.g., gastroparesis, kidney disease, coeliac disease

### *Prenatal care data*

Number and types of visits in each study group from referral to discharge after delivery:

- Type and number of visits with a dietitian (initial 60 min visit, 15-30 min follow-up visits, face-to-face, telephone or video)
- Number of visits with a midwife
- Number of visits with a nurse (individually)
- Number of visits with a nurse (in a group)
- Number of visits with an endocrinologist

Number of telephone contacts with an endocrinologist

Number of visits with an obstetrician  
Number of visits for ultrasonographic examination  
Number of visits including an interpreter (face-to-face, telephone or video)  
Body weight, kg at diagnosis and until delivery  
HbA1c, mmol/mol measured at diagnosis and until delivery  
Insulin-treated  
Time to insulin (days):  
- from study allocation until insulin prescription  
- from maternal GA  
Prescribed insulin, type, and dose (units/kg body weight)  
Prescribed antihypertensive medication, type, and dose  
Hospital admissions before delivery due to GDM  
Registered blood glucose measurements  
Preeclampsia

Labor data  
Induction of labour (yes vs no) and what weeks of gestation  
Preterm birth (defined as <37 weeks of gestation)  
Mode of delivery (vaginal delivery or caesarean section)

*Post-natal care*

Neonatal gestational age at birth  
Neonatal delivery weight, gram  
LGA  
SGA  
Macrosomia  
Jaundice  
Hospital days after delivery  
Neonatal hypoglycaemia  
Admission and number of days in NICU  
Stillbirth/neonatal death

#### **7.4 Socioeconomic baseline data**

The following self-administered questions on baseline demographics for background information will be sent out electronically after V1:

- Educational level
- Main occupation
- Civil status
- Household composition

## 8 Sample size determination

A 50% difference in the incidence of insulin therapy between the two study groups during the study period was defined as the minimally important difference for the primary outcome. The sample size estimation was based on a logistic regression model (outcome = group) and the following assumptions: An allocation ratio of 1:1; alpha = 0.05; 0.8 power, an incidence of insulin therapy of 30% in the usual care group and 15% in the intervention group in need of insulin therapy. The expected incidence in the standard care group is based on register data from Herlev Hospital in the period 2019-2022 showing that approximately 30% of the women with GDM referred to the hospital had been prescribed insulin. Since we are only investigating women with GDM with an estimated risk of insulin therapy above 20% based on our inclusion criteria), our analysis shows that it will result in an incidence of 50%. Thus, we aim to include 214 women (see table 3 for sample size estimations), but if fewer women are included, we will only test the main hypothesis for all participants whereas subgroup-analysis testing based on ethnicity (white\_nonwhite) will be exploratory.

**Table 3:** Sample size estimations

N Total	Power All	Power Subgroups
107	0.80	0.51
150	0.92	0.65
175	0.95	0.72
200	0.97	0.78
214	0.98	0.80

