## 4.4 Hypotheses

1. Hypothesis hierarchy for the primary outcome (objective 1):  
The type I error will be controlled in the strong sense using the following hierarchical (fixed sequence A-C) testing procedure. This is based on priority ordering of the hypotheses and testing them in this order until an insignificant result appears:
  - A. We hypothesise that intensive dietary therapy is superior to standard dietary care (control group) in reducing the need for initiating insulin therapy in all women with GDM. Superiority will be claimed if the difference between the two groups is equal to, or surpass, the minimal important difference (defined as 50% reduction in need for initiating insulin therapy in the intervention group compared with the control group) in favour of the intensive treated group, and if the P-value is  $< 0.05$ .
  - B. We hypothesise that intensive dietary therapy is superior to standard dietary care (control group) in reducing the need for insulin therapy in women with a white ethnic background with GDM. Superiority will be claimed if the difference between the two groups is equal

- to, or surpass, the minimal important difference (defined as 50% reduction in need for initiating insulin therapy in the intervention group compared with the control group) in favour of the intensive treated group, and if the P-value is  $< 0.05$ .
- C. We hypothesise that intensive dietary therapy is superior to standard dietary care (control group) in reducing the need for initiating insulin therapy in women with GDM with a non-white ethnic minority background. Superiority will be claimed if the difference between the two groups is equal to, or surpass, the minimal important difference (defined as 50% reduction in need for insulin therapy in the intervention group compared with the control group) in favour of the intensive treated group, and if the P-value is  $< 0.05$ .
2. Hypotheses for secondary outcomes (objective 2 and 3):
- We hypothesise that an intensive dietary intervention in comparison with standard dietary care will induce:
    - a clinically relevant limitation in gestational weight gain
    - a clinically relevant improvement in HbA1c
    - a clinically relevant delay in insulin therapy initiation
    - a clinically relevant limited maximal insulin dose (units per kg body weight)
    - a clinically relevant reduction in birth weight at delivery at term
    - a clinically relevant reduction in birth weight SD at delivery

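### Table 3's subgroup power of 0.80 at 214 women is stand-alone power; under the fixed sequence, hypothesis C (non-white women) has about 0.59 to 0.64, and less once the 50% criterion counts

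*Protocol*

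**What the plan says.** Protocol section 8 takes a halving of insulin use as the minimal important difference and lists "An allocation ratio of 1:1; alpha = 0.05; 0.8 power" with a model containing only the group term. It gives "an incidence of insulin therapy of 30% in the usual care group and 15% in the intervention group", then says of the women selected by predicted risk that "our analysis shows that it will result in an incidence of 50" percent. The target follows from this: "Thus, we aim to include 214 women (see table 3 for sample size estimations". Table 3 has one power column for all women and one for subgroups. Power for all women is already 0.80 at N=107. Power for subgroups is 0.51 at N=107 and reaches 0.80 only at N=214, the chosen size. If fewer than 214 women are included, "we will only test the main hypothesis for all participants whereas subgroup-analysis testing based on ethnicity" becomes exploratory.

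Section 4.4 orders three hypotheses: A in all women, B in white women, C in non-white women, "testing them in this order until an insignificant result appears". For each of the three, "Superiority will be claimed if the difference between the two groups is equal to, or surpass, the minimal important difference", a 50% reduction, and if p<0.05.

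The protocol gives no expected numbers of white and non-white women. Section 8 does not say whether the subgroup power allows for the sequence or for the 50% criterion.

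**The concern.** The subgroup column is the reason for 214 women rather than 107, and 214 is also the condition for confirmatory subgroup testing. A reader will naturally take 0.80 as the chance of a confirmatory answer in each ethnic group. Three things stand between that figure and C under the protocol's own rules: C is tested only if A and B are both significant, the claim also needs an observed reduction of at least 50%, and the figure depends on an equal ethnic split that is not stated.

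If the intervention truly halves insulin use in both groups, C is unreached or non-significant in about 4 trials in 10, even on the p-value alone. Such a result could be misread as no effect in non-white women.

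**Working it through.** **Inputs.** From section 8: 1:1 allocation, alpha 0.05, control incidence 50%, a 50% relative reduction (so 25% with the intervention), N=214. From section 4.4: the sequence A, B, C and the two-part claim rule. Assumed: two-sided testing, the same rates in both ethnic groups, and the ethnic splits shown below.

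**Step 1: reproduce Table 3.** For n women in total, the unpooled two-proportion formula is

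power = Φ( |p0 − p1| / √[2(p0(1−p0) + p1(1−p1))/n] − 1.96 ).

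With p0 = 0.50, p1 = 0.25 and n = 107: 0.25 / √(2 × 0.4375 / 107) = 2.765; 2.765 − 1.96 = 0.805; Φ = 0.79. Running it at N for the all-women column and at N/2 for the subgroup column gives:

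| N | Table 3, all / subgroups | Formula at N / at N/2 |
|---|---|---|
| 107 | 0.80 / 0.51 | 0.79 / 0.50 |
| 150 | 0.92 / 0.65 | 0.91 / 0.64 |
| 175 | 0.95 / 0.72 | 0.94 / 0.71 |
| 200 | 0.97 / 0.78 | 0.97 / 0.76 |
| 214 | 0.98 / 0.80 | 0.97 / 0.79 |

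All ten entries agree within 0.02. At 30% vs 15% the formula gives only 0.47 for all women at N=107, so 50% vs 25% is the scenario behind the table. The subgroup column is one subgroup of N/2 women, tested alone, on p<0.05 only.

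**Step 2: put C in the sequence.** B and C use different women and are independent. When both are significant in favour of the intervention, A almost always is too. So power for C in sequence ≈ power(B) × power(C):

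- table's own figure: 0.80 × 0.80 = 0.64
- formula that reproduces the table: 0.789 × 0.789 = 0.62
- simulation below: 0.59

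**Step 3: simulate the full rule.** Independent binomial counts in each ethnic group and arm, N=214, 50% vs 25%, likelihood-ratio test at p<0.05 in favour of the intervention, 1,000,000 trials per split. Each cell is B / C.

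| White / non-white | Tested alone, p only | In sequence, p only | Gate on p, 50% needed for the claim | p and 50% at every step |
|---|---|---|---|---|
| 107/107 | 0.77 / 0.77 | 0.77 / 0.59 | 0.51 / 0.39 | 0.39 / 0.26 |
| 128/86 | 0.85 / 0.70 | 0.85 / 0.59 | 0.53 / 0.46 | 0.42 / 0.28 |
| 86/128 | 0.69 / 0.85 | 0.69 / 0.59 | 0.53 / 0.37 | 0.39 / 0.28 |
| 150/64 | 0.90 / 0.56 | 0.89 / 0.51 | 0.53 / 0.45 | 0.43 / 0.27 |
| 64/150 | 0.56 / 0.90 | 0.56 / 0.51 | 0.50 / 0.30 | 0.36 / 0.27 |

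A is 0.97 on p alone and 0.52 once the observed 50% reduction is required. The drop is this large because the assumed true effect equals the threshold, so the estimate meets it only about half the time. A pooled z test agrees within 0.01 and a Wald logistic test within about 0.02.

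**Step 4: a larger true effect.** At 50% vs 20% (a 60% reduction) and 107/107, C in sequence is 0.84 on p alone, 0.72 with the 50% needed only for the claim, and 0.61 with it at every step.

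**The case against.** Table 3 is not arithmetically wrong, and section 8 never says that 0.80 is the chance of completing the sequence. Reporting power per hypothesis beside a fixed-sequence test is common. The sequence costs B almost nothing (0.769 alone and 0.765 in sequence at 107/107), type I error remains controlled, and A is well powered on p alone. The equal split can be inferred because subgroups at 214 equal all women at 107, and C is still 0.59 at 128/86. The wording of the stopping rule points to a gate on significance alone, so the lowest figures rest on the less natural reading. The 50% criterion also cuts A, so it is not specific to the subgroups.

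Much of this stands, and it limits the point. The fault is a figure that does not match the testing rule, not a wrong calculation. The gap between 0.77 and 0.80 for B comes from the choice of test, not from the sequence, and must not be presented as a sequence penalty. What does not stand is that stand-alone power is good enough here. The all-women hypothesis needed only 107, so the planned size was chosen for the gated hypotheses. C stays below 0.80 on p alone at every split examined. Section 4.4 also leaves room for doubt about the gate, since the sequence refers to significance while each claim needs both conditions.

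**Conclusion.** The point holds. The 0.80 at N=214 is the power of one subgroup of 107 women tested alone at p<0.05. For C under the fixed sequence, power on the p-value alone is 0.59 to 0.64 with equal subgroups and about 0.51 at 150/64 or 64/150. With the 50% criterion and a true reduction of exactly 50%, C is 0.39 at 107/107 (0.30 to 0.46 over the splits) if the gate is p alone, and 0.26 to 0.28 if both conditions apply at every step. A falls to 0.52 under the same criterion.

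These figures rest on 50% vs 25% in both ethnic groups, two-sided 0.05 and assumed splits. They would be lower at the 30% vs 15% that section 8 also lists: about 0.22 for C in sequence on p alone at 107/107. The correction should be made, but it does not call the test of A or the control of type I error into question.

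**What to change.** In section 8:

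1. Label the subgroup column as stand-alone power of one subgroup, p<0.05 only, assuming equal numbers of white and non-white women and 50% vs 25%.
2. Add power in sequence for B and C at N=214 over a range of splits, beside stand-alone power from the same test so that the two can be compared. With the likelihood-ratio test, B and C are 0.77 and 0.59 at 107/107; from 64/150 to 150/64, B runs from 0.56 to 0.89 and C from 0.51 to 0.59.
3. Add the same figures with the 50% criterion, and state whether the next hypothesis opens on p<0.05 alone or on p<0.05 plus the 50% reduction. Over these splits a p-only gate gives B 0.50 to 0.53 and C 0.30 to 0.46; both conditions at every step give B 0.36 to 0.43 and C 0.26 to 0.28. A is 0.52 either way.
4. Optionally, refer in section 4.4 to the section 8 rule that B and C are exploratory below 214 women. The rule is prespecified and conservative and can stay.

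The cost is a column label, a few recomputed figures and a sentence on the gate. No extra patients are needed, and randomisation and the tests do not change. The downside is a less favourable stated power for C, and for every hypothesis once the 50% criterion is counted.

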### 8.1 Study feasibility

Register data show that 200-300 women are diagnosed with GDM and treated in the Department of Obstetrics at Herlev Hospital yearly based on the current OGTT cut off value of  $\geq 9,0$  mmol/l for GDM in pregnancy (10). A high proportion of these women are expected to meet the criteria for study inclusion. Thus, it is realistic to expect that the study can recruit and include up to 214 women with GDM during the planned study recruitment period of approximately 1.5 years from October 2023 to December 2025.

## 9 Data management

### 9.1 Data handling

The study will comply with the Danish Data Protection Agency and the General Data Protection Regulation. All health-related matters and sensitive personal data will be handled in accordance with the Danish “Act on Processing of Personal Data”. Adequate blinding of all personal data during data processing and publication will be ensured. Data will be stored in coded form for 10 years after last participant has attended the last visit after which it will be fully anonymised.

All data will be entered directly into electronic case report forms (CRFs) using the software system REDCap licensed by the Capital Region in Denmark. Errors and corrections are logged as provided by the REDCap interface. It is possible to transport validated data from REDCap to e.g., a statistical program (e.g., SAS) for further statistical analysis. When data have been entered, reviewed, and verified the data will be frozen to prevent editing.

## 9.2 Data reporting and protection

Before initiating the study, acceptance from the Danish Data Protection Agency will be secured. All health-related matters and sensitive personal data will be handled in accordance with the Danish “Act on Processing of Personal Data”. All health-related matters and sensitive personal data (blood test result etc.) will be depersonalized. All participants will be given a study number referring to their personal information, which will be stored securely and separately. Adequate blinding of all personal data during data processing and publication will be ensured. Data will be stored in coded form in 10 years after last participant has attended the last visit, where after the data will be fully anonymised.

## 9.3 Source data identification and verification

All study-related information will be recorded, handled, and stored in a way that allows accurate reporting, interpretation, and verification. All questionnaire data will be collected electronically using the software system REDCap according to local standards for research projects in the capital region of Denmark. In addition, source data will be registered in REDCap on an ongoing basis and at the end of study. Data is stored in coded form for 10 years from last participant last visit. Hereafter, data will be fully anonymised.

## 9.4 Data reporting and protection

All information on study participants is protected according to the General Data Protection Regulation and the Danish Data Protection Agency (“Databeskyttelsesloven” and “Datatilsynet”), and the law of health and it will not be possible to identify any participant. None of the study-related blood samples or data will be stored or analysed in countries outside Denmark.

## 9.5 Protocol changes

Substantial amendments to this protocol may be implemented only after a favourable opinion of the Ethics Committee of the Capital Region, Copenhagen has been obtained. Amendments to the protocol are regarded as substantial if they have a significant impact on the safety, physical health, and mental integrity of the participants. If an event occurs related to the conduct of the study which may affect the safety of the participants, the study investigators may take appropriate measures to protect the participants against immediate hazards. The investigator will inform Ethics Committee of the Capital Region, Copenhagen of the new events and the measures taken as soon as possible.

